7 STUDY POPULATION

Potential subjects will be identified from the study unit's database of volunteers or via advertisement. Study-specific advertisements must be approved by the Institutional Review Board (IRB) before use. Potential subjects will be contacted by a dedicated recruitment officer who will invite them to participate in this study and schedule screening assessments.

The Investigator will maintain a confidential Screening Log of all potential study candidates, including each candidate's name or initials and the date and outcome of the screening process (e.g. enrolment in the study, reason for ineligibility). In addition, the Investigator will maintain an Enrolment Log of all subjects enrolled in the study, giving limited information about the subjects including screening number and assigned study number. The Screening Log and Enrolment Log together allow the Investigator to find out the identity of any subject when necessary.

Subjects will be considered enrolled in the study as soon as they have undergone their first assessment in Cycle 1.

7.1 Subject Numbers

Thirty-two (32) healthy pre-menopausal female subjects will be enrolled in Cohort 1. If Cohort 2 is required, a further 10 healthy pre-menopausal female subjects will be enrolled.

Subjects who do not complete the study may be replaced. A maximum of 10 additional subjects to replace subjects who withdraw may also be enrolled.

7.2 Selection Criteria

Individuals are eligible for the study if they meet all of the inclusion and none of the exclusion criteria. The criteria below will be assessed at a screening visit within 21 days before the expected start of Cycle 1. Continued subject eligibility will be verified at the clinic visit on Day 3 or 4 of Cycle 1 and again prior to the start of dosing in Cycle 2.

7.2.1 Inclusion Criteria

Study subjects must:

- 1 Healthy, female, aged 18 to 45 years inclusive (age at time of informed consent)
- 2 Regular (approximately) monthly menstrual periods
- 3 Be able and willing to understand and comply with the requirements of the study and give written informed consent
- 4 Have a body mass index (BMI) in the range 18.0 to 32.0 kg/m² and body weight not less than 40.0 kg
- 5 Be judged to be in good health, based on the results of medical history, physical examination, vital signs, 12-lead ECG, and clinical laboratory findings
- 6 Not be pregnant and not lactating, with no intention of pregnancy during study treatment

- 7 Agree to use two acceptable methods of birth-control, one of which is a barrier method with spermicide¹ (see [Section 8.8.2](#)) for the duration of participation in the study and 30 days after the last dose of study medication

7.2.2 Exclusion Criteria

Subjects must not:

- 1 Have been previously enrolled in this study or any other study with NT-814
- 2 Have clinically significant findings on physical examination at screening
- 3 Have any relevant medical history, in particular: liver or renal insufficiency, cholecystectomy, significant cardiac, vascular, pulmonary, gastrointestinal, endocrine, neurologic, hematologic, rheumatologic, psychiatric, or metabolic disturbances, any inflammatory illness or any other condition that the Investigator considers should exclude the subject
- 4 Have undergone bilateral oophorectomy and/or hysterectomy
- 5 Have positive serology for any of hepatitis B, hepatitis C, or human immunodeficiency virus (HIV)
- 6 Have any serum biochemistry and full blood count outside the normal reference ranges and considered by the Investigator to be of clinical significance, assessed at screening and on Cycle 1 Day 21/22. Hemoglobin must not be less than 11.0 g/dL at either screening or Day 21/22.
- 7 Have Stage 2 or higher hypertension (supine/semi-recumbent systolic blood pressure [SBP] >160 mmHg; diastolic blood pressure [DBP] >100 mmHg or Stage 1 hypertension (supine/semi-recumbent SBP 140–160 mmHg; DBP 90–100 mmHg associated with indication for treatment ie, evidence of end-organ damage, diabetes or a 10-year cardiovascular risk, estimated using a standard calculator, e.g. <https://qrisk.org/three/>, greater than 20%. Measurements will be based on the mean of duplicate values recorded at least 2 minutes apart and will be assessed at screening, on Cycle 1 Day 21 or 22 and pre-dose on Cycle 2 Day 1 or 2. Out of range measurements may be repeated once at each time point.
- 8 Have clinically relevant abnormal 12-lead ECG, including QT interval corrected for heart rate according to Fridericia (QTcF) >450 ms, QRS interval >120 ms, PR interval >220 ms, assessed at screening, on Cycle 1 Day 21 or 22 and pre-dose on Cycle 2 Day 1 or 2; if any value is out of range, 2 repeated assessments are permitted at that time point and the value will be based on the mean of the triplicate measure
- 9 Have a history of any grade of drug- or alcohol-use disorder according to Diagnostic and Statistical Manual of Mental Disorders 5 criteria³⁵ (or later edition if applicable) within 6 months before Screening or have a positive test result(s) for drugs of abuse (opiates including methadone, cocaine, amphetamines, methamphetamines, cannabinoids, barbiturates, and benzodiazepines) at screening, Cycle 1 Day 21 or 22, or Cycle 2 Day 1 or 2
- 10 Have a clinically significant acute illness within 7 days before first study drug administration

1 Acceptable methods of birth control are surgical sterilization of the subject's male partner, if he is the sole partner of that subject; surgical sterilization by bilateral tubal ligation, a non-hormonal intrauterine device (IUD) inserted at least one month before study drug administration and to remain in place for at least 30 days after the last dose of study drug; barrier methods such as male condom or cap, diaphragm or sponge with spermicide. An exclusively homosexual or abstinent lifestyle is also acceptable, provided it is maintained throughout the duration of the study and for 30 days afterwards.

- 11 Drink, on average, more than 6 cups of coffee or other caffeinated beverages daily (where each cup of coffee or beverage contains approximately 120 mg caffeine)
- 12 Smoke more than an average of 5 cigarettes (or equivalent) per day
- 13 Have used any non-permitted prior prescription, over-the-counter or herbal medication (see [Section 8.8.1](#))
- 14 Have a history of clinically significant drug and/or food allergies, particularly known allergy to any of the excipients used in the study medications (see [Section 8.1](#))
- 15 Have received an investigational drug (including vaccines) or used an investigational medical device within 3 calendar months before the first dose of study medication or be currently enrolled in an investigational study
- 16 Have had major surgery within 2 calendar months before first dose of study medication, or have surgery planned during the time the subject is expected to participate in the study
- 17 Have donated blood or experienced acute loss of a significant amount of blood within 3 calendar months before first dose of study medication
- 18 Have psychological and/or emotional problems that would render the informed consent invalid or limit the ability of the subject to comply with the study requirements
- 19 Have any condition for which, in the opinion of the Investigator, participation would not be in the best interest of the subject or that could prevent, limit, or confound the protocol-specified assessments.

7.3 Duration of Subject Participation

Subjects will be in the study for approximately 12 weeks, from screening through to the final Follow-up visit.

7.4 Early Subject Discontinuation or Withdrawal

Subjects may withdraw from the study at any time without stating a reason and without prejudice to further treatment. The Investigator may withdraw a subject from the study and discontinue study treatment and assessments at any time.

Early discontinuation of any subject who has given informed consent to participate will be recorded including the reason for discontinuation. The primary reason for a subject withdrawing prematurely will be selected from the following standard categories of early discontinuations:

- Failed to meet enrolment criteria (screen failure)
- Adverse event: clinical events occurred or laboratory results are reported that, in the medical judgment of the Investigator are grounds for discontinuation from participation, in the best interests of the subject
- Withdrawal of consent: the subject desired to withdraw from further participation in the study; the subject is not obliged to provide any reason for withdrawal of consent, but where a reason is given this will be recorded on the electronic case report form (eCRF)
- Protocol violation: the subject failed to adhere to the protocol requirements, e.g. the subject started taking a prohibited medication

- Lost to follow-up: the subject stopped coming for visits and study personnel were unable to contact the subject
- Other: the subject was withdrawn for a reason other than those listed above.

Any subject discontinuing study treatment, for example due to an AE considered related to study drug, may be asked to consent to continue in the study for relevant safety assessments and PK and PD sample collections. Priority must be given to safety assessments.

If a subject withdraws from the study, the Investigator should complete and report the observations as thoroughly as possible up to the date of withdrawal and the reason for withdrawal. The Investigator will ask all withdrawn subjects to consent to a follow-up examination, to check that they have come to no harm as a result of taking part in the study. Provided that subjects agree, they will undergo the standard medical examination and laboratory tests that they would have undergone had they completed it.

The Investigator will immediately (within 24 hours after discontinuation) notify the Sponsor. Subjects who withdraw from the study may be replaced at the discretion of the Sponsor if needed to achieve the objectives of the study.

8 STUDY MEDICATION AND ADMINISTRATION

8.1 Study Medication

The investigational medicinal product (IMP) is NT-814 in the free-base form, formulated as a 40-mg unit dose in a soft-gelatin capsule or matching placebo capsule. Inactive ingredients in both the active and placebo capsules are Capmul MCM EP, Labrasol ALF, Tween 80, Peceol and Vitamin E.

The physical, chemical, pharmaceutical formulation properties and characteristics of NT-814 are described in the IB³³.

8.2 Rationale for Selection of Doses in the Study

NT-814 has previously been administered to humans in a number of different dosage forms. As described in Section 4.4, the doses proposed in this study are currently being studied in women with hot-flashes associated with the menopause. The exposures associated with these doses in the soft gel capsule formulation have previously been shown to be associated with evidence of target engagement on the GnRH pathway.

8.3 Allocation to Treatment

The study will be conducted in a single-blind manner.

At screening, each subject will be assigned a unique screening number.

On Cycle 2 Day 1 or 2, subjects who continue to meet the eligibility criteria will be randomized to treatment groups as follows:

Cohort 1

NT-814 40 mg	8 subjects	Subject numbers 1001 to 1032
NT-814 80 mg	8 subjects	
NT-814 120 mg	8 subjects	
Placebo	8 subjects	

Cohort 2

NT-814 160 mg	8 subjects	Subject numbers 1033 to 1042
Placebo	2 subjects	

Cohort 1 will be enrolled first. Cohort 2 may be required dependent on review of the pharmacodynamic data from Cohort 1.

In the event that a subject is to be replaced, the replacement subject will be assigned the subject number of the subject she replaced to which 100 has been added and receive the same treatment as was planned for the original subject. Thus, Subject 1001 would be replaced by Subject 1101 and receive the treatment assigned to Subject 1001.

8.4 Study Treatment and Administration

All subjects will receive 4 capsules per day with placebo capsules being used to make up the count in subjects randomized to doses lower than 160 mg.

Dose	IMP Supply
Placebo:	4 x placebo capsules
40 mg:	1 x NT-814 capsule + 3 x placebo capsules
80 mg:	2 x NT-814 capsules + 2 x placebo capsules
120 mg:	3 x NT-814 capsules + 1 x placebo capsules
160 mg:	4 x NT-814 capsules

Subjects will take capsules at the assigned dose as a single oral dose on the mornings starting on Day 1 or 2 of Cycle 2 and continuing until the day prior to the final PD assessment on Day 21 or 22. Subjects will attend the clinic first thing in the morning for dosing and assessments, as per the schedule. The timing of each visit should be such that the dose of study medication is taken approximately 1-2 hours after having breakfast at home. Doses will be taken with 240 mL water.

Every effort should be made to administer study treatment on the planned dose and schedule. No dose modifications are permitted.

8.5 Packaging and Labelling

The investigational site will be provided with bulk drug supplies (NT-814 40 mg soft-gel capsules and placebo to match) in alu:alu foil blister strips, packaged and labelled according to local regulatory requirements. All doses are given in the study unit. Directions for preparing individual doses will be provided.

8.6 Handling and Storage

IMP must be dispensed and administered according to procedures described in the Study Manual. Only subjects enrolled in the study may receive IMP. Only authorized site staff may supply or administer IMP. All IMP must be stored in a secure area with access limited to the Investigator and authorized site staff. The bulk IMP must be kept in the original packaging and stored at ambient room temperature (15 – 25°C). Maintenance of a temperature log (manual or automated) is required whilst IMP is held at the study site.

8.7 Investigational Medicinal Product Accountability

In accordance with regulatory requirements, the Investigator is responsible for IMP accountability, reconciliation, and record maintenance. The Investigator or designated site staff (e.g., pharmacist) must maintain accountability records for IMP throughout the course of the study. The responsible person(s) will document the amount of IMP received and returned (on behalf of NeRRe) and the amount administered to subjects. The accountability unit for this study is a capsule. Discrepancies are to be reconciled or resolved. Procedures for final disposition of unused IMP will be provided.

The Investigator has overall responsibility for ensuring that the study treatment is received and managed at the study site in accordance with Good Clinical Practice (GCP). Limited responsibility may be delegated to a nominated study site representative; such delegation must be documented.

The Sponsor will be permitted upon request to audit supplies, storage and dispensing records and procedures.

8.8 Other Study Restrictions

Subjects must fast for 8 hours before clinical safety laboratory tests and strenuous exercise is prohibited for 3 days prior to any safety laboratory tests.

From 48 hours before the first dose until the follow-up visit, subjects must **not** consume products containing grapefruit or Seville oranges.

Throughout the dosing period subjects must be instructed to limit their caffeine intake to no more than 4 cups of coffee or equivalent beverages per day (equivalent to 120 mg caffeine per beverage).

Donation of blood to any institute other than the study unit is not allowed for the duration of the study.

Light alcohol consumption is permitted throughout the study – not more than 7 units per week.

Light smoking is permitted throughout the study – but not more than 5 cigarettes (or equivalent) per day.

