Subjects will return to the study unit in the morning of either the day of or the day following (or, in exceptional circumstances, 2 days following) the first day of their next menstrual cycle (the first day of bleeding; Cycle 2) and, after completion of baseline safety assessments, will be randomized to study treatment; they will then receive their first dose of study medication. They will attend the study unit daily in the morning for up to 20 further days to receive their study medication (so a total of up to 21 days dosing) with the last dose to be taken on the day prior to the Day 21 or 22 visit.

Additionally, on Day 3 or 4, Day 9 or 10, Day 15 or 16, and Day 21 or 22, blood samples for serum hormones will be collected and a single sample for measurement of plasma levels of NT-814 will also be collected. Blood samples for serum hormones (and PK) must be taken at the same time of day as the hormone samples were taken in Cycle 1 (± 1 hr).

The serum hormone sampling days relative to Day 1 of Cycle 2 will match the days samples were taken in Cycle 1 (relative to Day 1 of Cycle 1) within each subject (e.g. if the subject attended the clinic on Day 4 in Cycle 1, the hormone sample must be taken on Day 4 in Cycle 2; if they attended on Day 9 in Cycle 1 the hormone sample must be taken on Day 9 in Cycle 2, and so on).

If the subject unexpectedly cannot attend on Days 1-3 of their next menstrual cycle they can remain in the study and Cycle 2 will be scheduled for their next menstrual cycle. Clinic staff should keep in close

[figure not shown]
contact with the subject and instruct them to attend the clinic on Day 1 or 2 (or 3 in exceptional circumstances) of their subsequent menstrual cycle. Because of the delay between randomization and the previous safety laboratory assessments (performed Day 21/22 Cycle 1), these subjects will need to attend the clinic on Day 1 or 2 early enough to ensure that safety laboratory samples can be taken, and the results assessed prior to randomization and dosing.

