9 STUDY ASSESSMENTS AND PROCEDURES

Please see [Table 9-1](#) for the complete schedule of assessments. [Section 9.6](#) summarizes the order of procedures when more than one activity is scheduled for the same time point and permissible time windows.

Table 9-1 Schedule of Events

Day	Screening	Cycle 1					Cycle 2					Follow-up
	-21 ^a	1	3/4	9/10	15/16	21/22	1/2	3/4	9/10	15/16	21/22	35-38
Clinic visit (out-patient)	X		X	X	X	X	X					X ^e
Informed consent	X ^b											
Menstrual flow starts		X					X ^l					
Record dates of start of menstruation		X										X
Medical History	X											
Physical examination	X											X
Vital signs ^c	X					X	X ^f	X ^h	X ^h	X ^h	X	X
Oral or aural body temperature	X						X ^f					X
12-lead ECG	X					X	X ^f	X ^h	X ^h	X ^h	X	X
Weight	X					X	X					X
Serology ^d	X											
Drugs of abuse screen	X					X	X ^f					
Hematology and Clinical Chemistry	X					X	X		X		X	X
Serum pregnancy test	X					X						X
Urine pregnancy test							X ^f					
Sample for PD hormone assessment			X	X	X	X		X ^{h,i}	X ^{h,i}	X ^{h,i}	X ⁱ	
Sample for PK								X ^{h,j}	X ^{h,j}	X ^{h,j}	X ^j	
Randomization						X						
NT-814/placebo once daily							X					X ^g
Adverse Event / con med reporting ^k	X											X

- a Screening to be scheduled within 21 days of the anticipated start of the next menstrual cycle. This period can be extended if the menstrual period starts later than anticipated.
- b Informed consent can be obtained prior to the screening visit. The screening period starts from the date of the screening procedures, not from the date of consent.
- c Vital signs: systolic and diastolic blood pressure, pulse
- d Hepatitis B surface antigen, hepatitis B core antibody, hepatitis C antibody, human immunodeficiency virus
- e Daily clinic visits in the morning, starting on Day 1 or 2 of Cycle 2 and ending on Day 21/22.
- f Performed prior to the first dose
- g Doses administered in the morning, in the clinic ~1-2 hours after breakfast; starting on Day 1 or 2 of Cycle 2; last dose will be day prior to clinic visit on Day 21/22. Doses to be administered at the same time each day (±1hr).
- h Prior to administration of dose on the days shown
- i PD sample days must be the same relative to Day 1 on both Cycles 1 and 2
- j PK samples taken on same day/time as PD samples in Cycle 2
- k AEs and concomitant medication to be reported from the start of screening
- l Requires visual verification

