9.6 Priority Order of Study Assessments; Permitted Windows

Note the following with regard to sequence of tests and acceptable time windows.

- Informed consent can be obtained before the actual screening visit, with the 21-day screening period starting from the date of the screening visit and not the date consent is obtained
- Predose procedures on Day 1 or 2 of Cycle 2 must be completed before the first dose
- Assessments on Cycle 2 Days 3 or 4, 9 or 10, and 15 or 16 should be performed prior to dosing
- As far as possible, each subject should be dosed at the same time of day during the dosing period in Cycle 2; however, a window of ± 1 hr is permitted
- The serum hormone sampling days relative to Day 1 of Cycle 2 will match the days samples were taken in Cycle 1 (relative to Day 1 of Cycle 1) within each subject (e.g. if the subject attended the clinic on Day 4 in Cycle 1, the hormone sample must be taken on Day 4 in Cycle 2; if they attended on Day 9 in Cycle 1 the hormone sample must be taken on Day 9 in Cycle 2, and so on).
- Collection of samples for hormone assessment should be performed at approximately the same time of day throughout Cycles 1 and 2; however, a window of ± 1 hr is permitted
- Measurement of vital signs and ECG recordings should be avoided within 15 minutes after venipuncture and, therefore, should normally be done before blood sampling.

The Investigator may repeat tests, conduct tests other than those specified, and schedule additional visits in the event of a technical failure and/or if extra observations or samples of blood or urine are needed to monitor subject safety. These will not be considered protocol deviations.

Any deviation outside these permitted windows must be noted in the subject's clinic chart and eCRF.

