11.3.1 Baseline assessment

Descriptive statistics will be performed on relevant screening and baseline data (i.e. data collected prior to the treatment administration) and on demographic characteristics for each treatment group.

In general, baseline for safety assessments will be the last value recorded before the first dose of IMP. Baseline for PD assessments will be the time-matched value from Cycle 1.

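### On Cycle 2 Day 1/2 and Day 9/10, the 8-hour fast before safety bloods cannot be combined with a dose 1–2 hours after breakfast at home

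*Protocol*

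**What the plan says.** Section 8.8 sets the fasting rule for every safety laboratory test: "Subjects must fast for 8 hours before clinical safety laboratory tests".

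Section 8.4 sets the meal rule for every dosing visit: "The timing of each visit should be such that the dose of study medication is taken approximately 1-2 hours after having breakfast at home". Table 9-1, footnote g, repeats the interval without saying where breakfast is eaten: "Doses administered in the morning, in the clinic ~1-2 hours after breakfast".

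Table 9-1 schedules hematology and clinical chemistry on six occasions: screening, Cycle 1 Day 21/22, Cycle 2 Day 1/2, Cycle 2 Day 9/10, Cycle 2 Day 21/22 and follow-up. Day 1/2 and Day 9/10 of Cycle 2 are dosing mornings. Day 21/22 of Cycle 2 is not, since Section 6 ends treatment "with the last dose to be taken on the day prior to the Day 21 or 22 visit".

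The order of draw and dose is given in two places:
- Section 9.6: "Assessments on Cycle 2 Days 3 or 4, 9 or 10, and 15 or 16 should be performed prior to dosing".
- Section 6, for the first dosing visit: subjects, "after completion of baseline safety assessments, will be randomized to study treatment; they will then receive their first dose of study medication". For subjects whose Cycle 2 is deferred, they must come early enough that "safety laboratory samples can be taken, and the results assessed prior to randomization and dosing".

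Section 11.3.1 says that, in general, "baseline for safety assessments will be the last value recorded before the first dose of IMP".

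**The concern.** The fasting rule and the meal rule both apply on the two dosing mornings with safety bloods, and nothing in the protocol says which gives way. Each visit can resolve the conflict differently: the subject eats and is sampled fed, skips breakfast and is both sampled and dosed fasted, or is sampled fasted and then fed in the clinic.

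Laboratory change from baseline is a listed secondary endpoint, Section 11.3.2 assesses safety against baseline, and glucose is on the Table 9-2 panel. If the Day 1/2 sample is taken after breakfast, the baseline is fed while the later non-dosing samples are fasted. If practice varies between subjects, the baseline itself mixes the two states, and the protocol describes no field for time of last food. For deferred subjects the Day 1/2 results are also reviewed before randomization.

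Skipping breakfast is not neutral either. Section 4.3.1 reports that food lowered the soft-gel Cmax by about 71%, so giving the dose without breakfast departs from a condition the protocol set for exposure.

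**Working it through.** The protocol gives no figure of its own to reproduce. The check is timing arithmetic.

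**Inputs**
- Required fast: 8 h (Section 8.8).
- Breakfast to dose, B: about 1–2 h (Section 8.4; Table 9-1 footnote g).
- Draw to dose, g: zero or more, because the draw comes first (Section 9.6 for Day 9/10; Section 6 for Day 1/2).
- Subjects: 32 in Cohort 1, 42 with Cohort 2 (Section 7.1).

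**1. Fast achieved when breakfast is eaten at home before the visit.** Fast = B − g, which is at most B, so at most 1–2 h. The shortfall is at least 8 − 2 = 6 h to 8 − 1 = 7 h. The word approximately in Section 8.4 cannot absorb this. The ±1 h windows concern clock time of dosing and sampling, not time since food.

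**2. Could the draw be moved instead?** To reach 8 h after that breakfast, blood would have to be taken 8 − 2 = 6 h to 8 − 1 = 7 h after the dose. That breaks the pre-dose order and the morning visit.

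**3. Extent.** 2 of 6 laboratory occasions are affected: 2 × 32 = 64 scheduled draws, or 2 × 42 = 84. The other four occasions involve no dose and no conflict.

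**4. Effect on change from baseline if both dosing-day samples are fed.** The baseline (Day 1/2) is fed. The three later occasions compare as follows:

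| Occasion | State | Comparison with baseline |
|---|---|---|
| Day 9/10 | fed | like with like |
| Day 21/22 | fasted | fed to fasted |
| Follow-up | fasted | fed to fasted |

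So 2 of 3 post-baseline comparisons are mixed. The protocol gives no size for the resulting shift in glucose, and none is claimed here.

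**5. Effect of skipping breakfast instead.** With a 71% reduction in Cmax by food, the fasted value is 1/(1 − 0.71) = 1/0.29, about 3.4 times the fed value. This is an upper bound, since breakfast 1–2 h earlier may not match the fed condition tested. The corresponding AUC reduction was only 9%.

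**6. Does a fasted draw followed by breakfast and then dosing fit the dosing window?** Let T be the sampling time and assume breakfast takes 15–30 min.
- 15 min: dose between T + 1.25 h and T + 2.25 h.
- 30 min: dose between T + 1.5 h and T + 2.5 h.

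To stay within ±1 h of the usual dose time D, D must lie between T + 0.25 h and T + 3.25 h (15 min), or between T + 0.5 h and T + 3.5 h (30 min). Both hold for D between T + 0.5 h and T + 3.25 h, so the sequence is feasible if the site sets the usual dose time in that range.

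**The case against.** The strongest reply is that the two rules differ in force: the fast is mandatory, whereas the meal timing is expressed as something that should happen, approximately. A site that respects the mandatory rule would draw fasted, then feed, then dose. That meets the fast, the pre-dose order and footnote g, and only the words about eating at home stand in the way. For deferred subjects the laboratory turnaround already sits between draw and dose. If it exceeds about 2 h (the protocol does not say), breakfast would have to come after the draw anyway. All this is fair, but the workaround still departs from Section 8.4 as written, and nothing ensures that it is done for every subject.

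The Day 1/2 laboratory cell in Table 9-1 also lacks the footnote marking pre-dose procedures. This stands as a qualification. For non-deferred subjects the pre-dose draw rests on Section 6 and on the baseline rule in Section 11.3.1. For deferred subjects, and for Day 9/10, it is explicit.

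The consequence is limited. Table 9-2 has no lipids or insulin, liver enzymes are the laboratory signal the protocol highlights, and the safety analysis is descriptive. The laboratory eligibility criterion is applied at screening and Cycle 1 Day 21/22, which have no conflict. These points stand and set the weight of the finding. The draw counts show how many samples fall under the conflict, not how many are biased.

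Finally, a fasted Cycle 2 Day 9/10 visit differs from the Cycle 1 Day 9/10 visit, where no fast is required, and hormones are compared between the two. Section 8.8 already imposes that difference, in all arms alike, so resolving the conflict in favor of the fast adds nothing new.

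**Conclusion.** The contradiction is real and should be corrected. If Section 8.4 is followed, the fast before the Cycle 2 Day 1/2 and Day 9/10 safety bloods is at most about 2 h instead of 8 h, on 2 of 6 laboratory occasions in every subject who attends them. This rests on both draws preceding the dose.

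The weight is modest. It concerns within-arm change in prandially sensitive analytes, glucose above all, in a secondary descriptive outcome. Placebo follows the same schedule, so the comparison with placebo is not systematically biased, and the primary hormone endpoints are not affected.

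**What to change.** Amend Section 8.4 and Table 9-1 footnote g. On Cycle 2 Day 1/2 and Day 9/10, subjects in all arms arrive fasted, safety blood is drawn, breakfast is given in the clinic, and the dose follows 1–2 h later. Set the usual dose time about 0.5 to 3 h after the usual sampling time, so that these two mornings stay inside the ±1 h dosing window. For deferred subjects, time breakfast around the return of the laboratory results.

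The alternative is to waive the fast on those two days and use the fasted Cycle 1 Day 21/22 sample as the reference for glucose. It is weaker: the Day 9/10 change would then compare a fed value with a fasted one, and in deferred subjects the reference is about one cycle older.

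Under either option, record the time of last food at each of these draws. The choice belongs to the sponsor and investigator. The cost is a short amendment, one eCRF field and, under the first option, a longer clinic visit on two mornings.
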